13.9 Analysis Plan

The analysis plan has five components. First, we will compare primary and secondary endpoints in cohort participants at sites randomized to the intervention or the control condition. Second, we will assess whether the intervention, in comparison with the control condition, was associated with “off-target” effects at ICCs (number of unique persons tested for HIV and number of HIV-positive persons diagnosed). Third, we will conduct a mixed methods evaluation of the HIV care incentives. Fourth, we will evaluate the impact of the HIV care incentives on PWID and MSM community-level outcomes with a dedicated RDS survey. Fifth, we will evaluate the cost-effectiveness of the HIV treatment incentive intervention.

13.9.1 Analysis plan for primary outcome

In the primary analysis, we will use an intent-to-treat, missing equals failure approach. The primary outcome will be the proportion of participants who have survived with a suppressed viral load (HIV RNA <150 c/mL) at the 12-month cohort follow-up visit. Participants that die prior to the 12-month visit or miss the 12-month visit will be considered failures in the analysis. The primary analysis will be at the site-level and will use a two-stage procedure beginning with fitting an individual-level logistic regression model with terms for each matched pair and individual-level viral suppression at the baseline visit (HIV RNA <150 copies/mL), but ignoring the intervention effect. The model computes the expected number of events in each cluster. The observed and expected number of events in the two clusters in each matched pair are compared and if there is no intervention effect these values will be the same. An adjusted prevalence ratio and 95% confidence interval will be calculated by estimating the mean within-pair difference of the natural log transformed adjusted prevalences by arm. The exponentiated difference is the ratio and a paired t-test will be used for significance testing. An adjusted prevalence difference and 95% confidence interval will be calculated in a similar manner, estimating the mean within pair difference of the non-transformed prevalences by arm. Analysis of the primary outcome will also be stratified by viral suppression status at baseline (HIV RNA <150 copies/mL). In this site-level one-stage approach, we will calculate the difference in the proportion with suppressed viral load within each matched pair among strata defined by baseline viral suppression. We will calculate the unweighted mean of the pair-wise difference with a 95% confidence interval and use a paired t-test to test the hypothesis that within each stratum the observed difference is statistically different from zero. We will further explore whether there is statistically significant interaction by baseline viral suppression status and intervention effect.

Primary outcome sensitivity analyses

We will conduct several supplemental analyses to assess whether inferences are sensitive to different analytic specifications. First, we will conduct an analysis in which participants who

miss the 12-month visit (but are not known to be deceased) will be excluded (missing ignored), and death or non-suppression of the HIV RNA at month 12 will be considered failure. Second, we will conduct an analysis that includes only individuals that complete the 12-month visit (deaths and missing ignored) and non-suppression of the HIV RNA at month 12 will be considered failure. In a third sensitivity analysis, we will consider adjusting for additional potential confounders using the same two-stage procedure described above (6). We will only consider factors measured at the baseline visit (no post-randomization measures) that have a large (odds ratio >2 or <0.5) and statistically significant ($p<0.05$) association with the intervention status and the outcome. Fourth, we will conduct pre-specified analyses that are stratified by key population (PWID and MSM).

13.9.2 Secondary outcomes

Secondary binary outcomes including i) survival with suppressed viral load at other time points (6, 18, and 24 months), ii) proportion with at least one suppressed viral load during follow-up, iii) proportion retained to HIV care (defined as the proportion with at least one visit to the ART center per 6-month follow-up interval), and iv) mortality will be analyzed similarly resulting in pair-wise differences in proportions with a two-stage procedure for confounder adjustment, if appropriate (criteria for confounders outlined in prior section).

For two other secondary outcomes, we will use similar pair-matched cluster approaches with a two-stage procedure for confounder adjustment. First, we will compare risk of initiating ART at intervention vs. control sites (among the subset that is ART-naïve at baseline) using a Cox proportional hazards model. Second, we will compare ART possession ratio (defined as number of days covered by ART dispensations divided by the number of days under observation) by calculating a mean difference between intervention and control conditions.

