4. PROTOCOL SUMMARY

Strategies to Improve the HIV Care Continuum among Key Populations in India: a Cluster Randomized Trial

Purpose:

People who inject drugs (PWID) and men who have sex with men (MSM) have a high HIV prevalence in India. In prior work, we found that key population-specific integrated care centers (ICCs), which provide HIV testing, risk reduction services, and assistance linking HIV-positive persons to government HIV clinics, increased HIV testing rates and were popular and acceptable to PWID and MSM. However, by itself, the ICC intervention was not associated with improvements in the HIV care continuum among HIV-positive persons. The purpose of this trial is to evaluate the effectiveness of non-cash HIV care incentives – a demand creation strategy – to improve progress on the care continuum among HIV-positive PWID and MSM in India.

Design:

Matched-pair cluster randomized trial.

Study Population:

HIV-positive ICC clients who are 18 years of age or older, antiretroviral therapy (ART)-naïve or have taken ART for less than 12 months, and do not receive HIV care in the private sector.

Study Size:

The study will be conducted at 16 sites (clusters) and we aim to enroll up to 150 participants at each site (2400 participants overall).

Treatment Regimen:

Participants at sites randomized to the intervention will (in addition to receiving usual linkage services provided by ICCs) be eligible to receive incentives (non-cash vouchers for goods) for achieving HIV care milestones, including visiting a government HIV clinic prior to ART initiation, initiating ART, attending HIV treatment motivational interview sessions, and collecting timely ART refills.

Participants at sites randomized to the control condition will receive usual linkage to care services provided by ICCs, including outreach worker assistance with linkage to HIV treatment and reminders to remain in care.

Study Duration:

The study duration will be approximately 48-54 months. Ethnography and preparatory work at the sites will take 6 months. Participants will be enrolled over 12 months and then followed for a 24-month intervention phase. Finally, an epidemiologic survey will be conducted at all sites at the conclusion of the intervention phase that will extend another 6-12 months.

Primary Objective:

To determine if HIV care incentives increase survival with viral suppression at 12 months among

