8.3 Participant Retention

Once a participant enrolls in the cohort study, the study site will make every effort to retain

him/her for the full study period (24 months), to minimize possible bias associated with loss-to-follow-up. Retention rates of 80% at 24 months are targeted among non-deceased participants. Study site staff are responsible for developing and implementing local standard operating procedures to target this goal. Components of such procedures include:

- Thorough explanation of the study visit schedule and procedural requirements during the informed consent process and re-emphasis at each study visit.
- Collection of detailed locator information at the baseline visit, and active review and updating of this information at each subsequent visit.
- Use of mapping techniques to establish the location of participant residences and other locator venues.
- Use of appropriate and timely visit reminder mechanisms to retain participants.
- Immediate and multifaceted follow-up on missed visits.
- Mobilization of trained outreach workers or “tracers” to complete in-person contact with participants at their homes and/or other community locations.
- Regular communication with the study community at large to increase awareness about HIV/AIDS and explain the purpose of HIV treatment research and the importance of completing research study visits.

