10. STUDY PROCEDURES/EVALUATIONS

10.1 Clinical Evaluations and Procedures

Clinical evaluations and procedures for study cohorts in cluster randomized trial

Eligible participants who meet inclusion criteria and provide written informed consent will be enrolled in the local cohort. Cohort participants will complete a baseline study visit, most often on the day of screening, and will be asked to complete follow-up visits at 6 months, 12 months, 18 months, and 24 months, for a total of 5 study visits. However, due to delays from the COVID-19 pandemic, not all participants were able to complete the 18- and 24-month visits. Detailed information on the evaluation and procedures of study visits are shown in **Appendix I**. Study visits will include the following evaluations:

- Biometric capture (fingerprint) to confirm identity
- Blood draw, laboratory assessments described below
- Collection of contact and locator information
- Interviewer-administered survey covering the following domains
 - Demographics
 - Quality of life
 - Engagement/experience with HIV care
 - ART adherence
 - Beliefs about ART
 - Alcohol and drug use
 - Injection- and sex-related risk behaviors
 - Depression symptoms
 - Health care utilization
 - Fentanyl and overdose (from 18 months onward)
- Abstraction of information from government ART book

Clinical evaluations and procedures for mixed methods evaluation of treatment incentives

We will query cohort participants at incentive sites about their experiences with and perceptions of treatment incentives in the 24-month visit interview. Additionally, individuals eligible for the qualitative component will be invited to participate in in-depth interviews (IDI). IDIs will use a semi-structured format to address the following domains:

IDIs with ICC clients at intervention sites

- Perceived purpose of the incentive program
- Process of learning about the incentive program
- Experiences with receiving incentives
- Opinions about the value of incentives and how frequently incentives could be earned
- Impact of incentive program on client opinions and beliefs about HIV care

IDIs with ICC staff

- Familiarity with the incentive program
- Perceived purpose of the incentive program
- Challenges with implementing the incentive program
- Good and bad things about the incentive program
- Opinions about how the program affected HIV-positive clients' behaviors

Clinical evaluations and procedures for RDS survey

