Protocol revisions due to COVID-19: Cohort study participant enrollment was completed in October, 2018. Study activities (follow-up visits and incentive intervention) were suspended indefinitely in March 2020. At the time research activities were suspended, all participant visit windows had closed for the 6- and 12-month follow-up visits. However, 65 and 959 participants had not completed the 18- and 24-month visits, respectively, but had not reached or were within the visit window. Because of this, in Protocol Version 2.0 we revised the primary endpoint from 24 months to 12 months. Data that was collected at 18 and 24 months will be considered in secondary and sensitivity analyses.

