13.4 Sample Size Considerations

We calculated power for comparing the primary endpoint within matched cluster pairs, *survival with suppressed viral load, defined as HIV RNA <150 copies/mL in plasma or serum, at 24 months*, among the cohorts of HIV-positive study participants. Cluster-randomized designs require consideration of the between-cluster coefficient of variation (k), a measure of variation between clusters. In general, the more variability in outcome between clusters, the larger the sample size required to detect a given difference. The coefficient of variation in a matched study needs to take into account the matching correlation (k_m), in other words how much of a reduction in pair variability is accomplished by matching. More successful matching is associated with lower k_m values. We calculated the k_m using baseline RDS data from a prior trial for a hypothetical set of matched pairs based on the proposed matching criteria for this trial as described above. The values of k_m ranged from 0.08 to 0.15 when considering RDS-II weighted and unweighted estimates of the outcome of interest. In addition to consideration of k_m , we also considered other factors specified by the sample size formula from Hayes et al. (6):

$$c = 2 + (Z_{\alpha/2} + Z_{\beta})^2 [\pi_0(1 - \pi_0)/n + \pi_1(1 - \pi_1)/n + k_m^2(\pi_0^2 + \pi_1^2)](\pi_0 - \pi_1)^2$$

where π_0 and π_1 are the true population proportions in the absence and presence of the intervention, respectively, n is the number of individuals within each cluster, $Z_{\alpha/2}$ and Z_{β} are the standard normal distribution values corresponding to the upper tail probabilities of $\alpha/2$ and β , respectively and k_m is the coefficient of variation within matched pairs.

Within our calculations, we varied the k_m from 0.10-0.20 based on our preliminary data, the sample size per cluster from 50-150 to account for varying levels of loss to follow-up, and the outcome prevalence in control condition clusters from 25-45%. The number of cluster pairs needed was relatively insensitive to the prevalence of outcome in the control group and the cluster size as long as the sample size was >70 per cluster.

Figure 2 shows the number of cluster pairs needed (y-axis) to provide 80% power to detect differences of 0.05 to 0.30 (x-axis) across a range of k_m values (different colored lines) assuming a sample size of 150 per cluster, two-sided alpha=0.05, and 25% outcome prevalence in the

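### Section 13.9.2 sets no denominator for 18- and 24-month suppression; on its natural reading, 959 participants whose 24-month visit was not due or still in window at the March 2020 suspension count as failures

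*Combined protocol and SAP*

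**What the plan says.** Section 13.9.2 groups the secondary binary outcomes in one sentence, beginning "Secondary binary outcomes including i) survival with suppressed viral load at other time points (6, 18, and 24 months". It also lists at least one suppressed viral load, retention and mortality, and says all are analysed similarly to the primary, by pair-wise differences with a two-stage adjustment where appropriate.

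For the primary, 13.9.1 specifies intent-to-treat with missing equals failure: "Participants that die prior to the 12-month visit or miss the 12-month visit will be considered failures in the analysis". Two sensitivity analyses relax this. The first concerns participants who "miss the 12-month visit (but are not known to be deceased) will be excluded (missing ignored"; the second keeps only those who completed the 12-month visit. Neither mentions another time point.

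Section 13.1 records that follow-up and the incentive intervention stopped in March 2020. By then every 6- and 12-month window had closed, but "65 and 959 participants had not completed the 18- and 24-month visits, respectively, but had not reached or were within the visit window". For that reason the primary endpoint moved from 24 to 12 months. The same paragraph says the 18- and 24-month data already collected will be considered in secondary and sensitivity analyses. Section 10.1 adds that "not all participants were able to complete the 18- and 24-month visits". Section 13.2.2 keeps 18- and 24-month survival with suppression as secondary endpoints without defining an analysis set.

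**The concern.** A participant whose 24-month visit was not yet due in March 2020 has not missed it. Enrolment ended in October 2018 (13.1). If visits are counted from enrolment, the last 24-month visits fell due around October 2020, about seven months after the suspension. Scoring such people as failures measures when they joined, not how they fared.

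Moving the primary endpoint protected the primary analysis, but 13.9.2 was not adapted for the time points left behind. If the primary's rule is carried over, 24-month prevalence is too low in both arms and the prevalence difference shrinks. Any cost-effectiveness result based on 24-month suppression, which 13.9.3 offers as an example, would inherit that difference. If the affected share differs between arms, the ratio is distorted too, in whichever direction the imbalance runs.

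If the rule is not carried over, the plan has no missing-data rule for these time points. The analyst of an unmasked trial (13.6) would then choose among all-enrolled, closed-window and completer sets after the data are in.

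**Working it through.** **Inputs**
- Visits not completed, and not yet due or still in window, at suspension: 959 at 24 months and 65 at 18 months (13.1).
- Enrolment: the actual number is not given. Section 4 says "we aim to enroll up to 150 participants at each site (2400 participants overall"; 2400 is therefore a maximum, and any share computed from it is a minimum.
- Contrasts: 25% v 33% and 40% v 50%, both with k_m = 0.10 and 8 pairs. Section 13.4 is still written for the 24-month endpoint, so these are the right contrasts to use.

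**Plan's own figure.** The 13.4 formula, with the squared difference read as a divisor, is c = 2 + (1.96 + 0.84)² × [p0(1−p0)/n + p1(1−p1)/n + k_m²(p0² + p1²)] / (p0−p1)². For 25% v 33% and n = 150 the bracket is 0.00125 + 0.00147 + 0.00171 = 0.00444. So c = 2 + 7.85 × 0.00444/0.0064 = 7.44, which rounds up to 8 pairs. The plan's statement reproduces; 8 pairs give 83.7% power.

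**Share affected**
- 24 months: s = 959/2400 = 40.0%. With 2200 enrolled it is 43.6%, and with 2000 it is 48.0% (both enrolments are assumptions).
- 18 months: 65/2400 = 2.7%.

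**Effect of counting the 959 as failures.** Apparent prevalence is (1 − s) times the prevalence among everyone else. Assume the 959 would have been suppressed as often as the rest, and that s is equal in both arms.

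| Enrolled | 25% v 33% appears as | Difference (true 8.0) | 40% v 50% appears as | Difference (true 10.0) |
|---|---|---|---|---|
| 2400 | 15.0% v 19.8% | 4.8 points | 24.0% v 30.0% | 6.0 points |
| 2200 (assumed) | 14.1% v 18.6% | 4.5 points | 22.6% v 28.2% | 5.6 points |
| 2000 (assumed) | 13.0% v 17.2% | 4.2 points | 20.8% v 26.0% | 5.2 points |

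At 2400 enrolled, the apparent 24-month proportion cannot exceed 60.0% even if everyone else is suppressed. At 18 months, 8.0 × (1 − 0.027) = 7.8 points.

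**Ratio.** With equal shares, (1 − s) cancels: 0.33/0.25 = 1.32 before and after. With unequal shares it does not. If 35% of one arm and 45% of the other were affected (an assumption; the split is not given) and there were no true effect, the apparent ratio would be 0.65/0.55 = 1.18, or 0.55/0.65 = 0.85 with the arms exchanged. At 25% true suppression that is 16.25% v 13.75%, a false 2.5 points.

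**Power.** For 25% v 33% with 8 pairs, the 13.4 formula gives 64.8% under the carried-over rule with n = 150. Leaving out the 959 leaves at most (2400 − 959)/16 = 90 per site on average, which gives 69.8%. The two are level at about 77 per site. Because 90 still includes visits completed in windows that were open, the closed-window number is lower by an unknown amount.

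**The case against.** The strongest reply is that the plan nowhere says the 959 are failures. The word *similarly* leads into pair-wise differences and the two-stage procedure, so it may name only the estimator. The same sentence covers mortality, for which missing equals failure has no direct meaning. Section 13.9.1 fails people who miss a visit, whereas 13.1 describes the 959 as not yet due or in window, and its remark about data already collected could suggest an available-data analysis. All of this stands as a reason not to call the rule express. It does not close the gap. For the same endpoint at another time point, carrying over the primary's rule remains the most direct reading. The available-data reading names no set, and does not say what happens to deaths, to closed-window misses, or to visits completed in a window still open.

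A second reply is that the ratio is untouched when shares are equal across arms. That is correct. But 13.9.2 names differences in proportions as the result for these outcomes, and nothing in the documents shows that shares are equal.

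A third is that a closed-window set drops viral loads that were in fact measured. That also stands, which is why those visits belong in a sensitivity analysis. In an open window, however, a result exists only for those who came early, so adding them to the main set would select on attendance.

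Finally, these are secondary time points and the sponsor moved the primary for this very reason. That limits the importance of the point but does not supply the missing rule.

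**Conclusion.** The point holds as a gap in 13.9.2 that should be fixed. At least 40.0% of participants had no 24-month visit for reasons of calendar time, the plan gives them no denominator rule, and the rule it would most naturally borrow counts them as failures. At the maximum enrolment, 8.0 points would then appear as 4.8; lower enrolment makes it smaller. This assumes that the 959 would have been suppressed as often as the rest, that the share is equal across arms, and that the borrowed rule is the one applied. The 18-month effect is small.

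Stronger conclusions that a reader might draw are not supported:
- *The plan expressly fails the 959.* It does not; this is the natural reading of a silent text.
- *The trial's main result is compromised.* All 12-month windows had closed, so the primary is unaffected.
- *The 24-month effect is biased towards no effect on every scale.* The ratio is unchanged with equal shares and could move either way with unequal ones.
- *The dilution can be narrowed using the retention goal.* Section 8.3 says "Retention rates of 80% at 24 months are targeted among non-deceased participants", but that is a target. The documents do not say how many of the 959 had already died or been lost.
- *Small closed-window sites call for a different estimator.* The 13.4 remark about "cluster size as long as the sample size was >70 per cluster" concerns the number of pairs needed and sets no such threshold.
- *A closed-window set restores power.* It may not; the gain is an undistorted estimate.

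**What to change.** Amend 13.9.2 as follows.

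1. For 18 and 24 months, limit the main-analysis denominator to participants whose scheduled visit window had closed before the suspension, whether or not they attended. Apply missing equals failure within that set. The flag depends only on scheduled dates, not on attendance or outcome.
2. State the anchor date and window width behind the flag. The only width in the documents is the ±14 days for the bonus payment in 16.7, which is not described as an analysis window.
3. Add a sensitivity analysis that also includes visits completed in windows still open at suspension, and extend the missing-ignored analysis of 13.9.1 to these time points.
4. Report not-due, open-window and closed-window counts by arm and pair, so that any imbalance is visible.
5. State how the same participants are handled for at least one suppressed viral load, which draws on the 18- and 24-month visits, and use the same set for any 24-month cost-effectiveness outcome.

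The cost is a few sentences of SAP text and one derived flag, with no new data and no change to the primary analysis. The downside is a smaller 24-month denominator: at most about 90 per site on average, lower by an amount the documents do not give, and possibly uneven across sites. A pair with few closed windows would be estimated poorly; the counts in item 4 would show it.
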